#### **9.4.5. Safety Monitoring**

Lilly will periodically review evolving aggregate safety data within the study by appropriate methods.

If a study subject experiences elevated ALT  $\geq 3X$  ULN, ALP  $\geq 3X$  ULN, or elevated TBL  $\geq 2X$  ULN, clinical and laboratory monitoring should be initiated by the investigator. Details for hepatic monitoring depend upon the severity and persistence of observed laboratory test abnormalities. To ensure subject safety and comply with regulatory guidance, the investigator is to consult with the Lilly CRP regarding collection of specific recommended clinical information and follow-up laboratory tests. See [Appendix 4](#).

Any enrolled subject who is HBcAb+ will undergo periodic monitoring of HBV deoxyribonucleic acid (DNA) per the Schedule of Activities.

In addition to the above, any enrolled subject who is HBcAb+ and who experiences an elevated ALT or AST level  $>3X$  ULN must undergo HBV DNA testing. If the HBV DNA PCR test is negative, the investigator should consult with the Lilly-designated medical monitor regarding further management of the subject.

If the result of any HBV DNA PCR test is positive at any time, the subject must be discontinued from the study and should receive appropriate follow-up medical care, including consideration for antiviral therapy. A specialist physician in the care of patients with hepatitis (for example, infectious disease or hepatologist subspecialists) should be consulted and potentially start antiviral therapy.

In the event that safety monitoring uncovers an issue that needs to be addressed by unblinding at the group level, only members of a sponsor assessment committee (an advisory group for this study formed to protect the integrity of data; refer to Section [10.3.7](#)) should conduct additional analyses of the safety data.

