- hematologic: absolute neutrophil count  $\geq 1.5 \times 10^9/L$  ( $\geq 1.5 \times 10^3/\mu L$  or  $\geq 1.5$  GI/L), platelet count  $\geq 100 \times 10^9/L$  ( $\geq 100 \times 10^3/\mu L$  or  $\geq 100$  GI/L), hemoglobin level  $\geq 10.0$  g/dL ( $\geq 100$  g/L), lymphocyte count  $> 500$  cells/ $\mu L$  ( $> 0.50 \times 10^3/\mu L$  or  $> 0.50$  GI/L), and total white blood cell count  $\geq 3.0 \times 10^9/L$  ( $\geq 3.0 \times 10^3/\mu L$  or  $\geq 3.0$  GI/L)
  - chemistry:
    - serum creatinine, aminotransferase (ALT), and aspartate aminotransferase (AST) levels  $\leq 2 \times$  upper limit of normal (ULN)
    - total bilirubin level (subjects with Gilbert's syndrome must have serum direct bilirubin  $< 1.5$  mg/dL) and alkaline phosphatase (ALP)  $< 1.5 \times$  ULN
- [8] are reliable and willing to make themselves available for the duration of the study, and are able and willing to follow study procedures

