## 8. Discontinuation Criteria

### 8.1. Discontinuation from Study Treatment

#### 8.1.1. *Permanent Discontinuation from Study Treatment*

Discontinuation of the investigational product for abnormal liver tests **should be considered** by the investigator when a subject meets one of the following conditions after consultation with the Lilly designated medical monitor and consideration of the clinical status of the subject (including patients with Gilbert's syndrome):

- alanine aminotransferase (ALT) or aspartate aminotransferase (AST) >8X upper limit of normal (ULN)
- alanine aminotransferase or AST >5X ULN for more than 2 weeks
- alanine aminotransferase or AST >3X ULN and total bilirubin level (TBL) >2X ULN or prothrombin time >1.5X ULN
- alanine aminotransferase or AST >3X ULN with the appearance of fatigue, nausea, vomiting, right upper-quadrant pain or tenderness, fever, rash, and/or eosinophilia (>5%)
- alkaline phosphatase (ALP) >3X ULN
- alkaline phosphatase >2.5X ULN and TBL >2X ULN
- alkaline phosphatase >2.5 ULN with the appearance of fatigue, nausea, vomiting, right quadrant pain or tenderness, fever, rash, and/or eosinophilia (>5%)

Subjects who discontinue the investigational product early will continue in the study according to the Schedule of Activities (Section 2).

Investigational product is to be discontinued for patients who experience clinically significant systemic hypersensitivity events (such as anaphylaxis) following administration of investigational product.

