### **9.4.4. Other Tests**

#### **9.4.4.1. Chest Radiography and Tuberculosis Testing**

Posterior-anterior view and lateral view (unless local standards dictate 1 view) chest radiography will be obtained at screening (Visit 1), unless the radiographs or medical report from chest radiography performed within 3 months before initial screening (per local standard of care for TB evaluation) are available to the investigator for review.

In addition, subjects will be tested as indicated in the Schedule of Activities (Section 2) for evidence of active or latent TB. A positive TB test result is indicated by a purified protein derivative (PPD) skin test response  $\geq 5$  mm induration documented approximately 48 to 72 hours after test application (regardless of Bacillus Calmette-Guerin vaccination history). In countries where the QuantiFERON-TB Gold test (or equivalent) is available and is preferred (in the judgment of the investigator) as an alternative to the PPD skin test for the evaluation of TB infection in a subject, that test may be used instead of the PPD test. If the QuantiFERON-TB Gold test is indeterminate, 1 retest is allowed. If the retest is indeterminate, then the subject is excluded from the study.

Subjects with documentation of negative TB test results within 3 months before initial screening may not need to repeat TB testing at screening (Visit 1) based on judgment of the investigator. Documentation of this previous test result must include a record of the size (in millimeters) of the induration response. A PPD test recorded as “negative” without documenting the size of induration (in millimeters) will not be acceptable and will require a retest.

However, subjects with a PPD skin test response  $\geq 5$  mm induration or a positive QuantiFERON-TB Gold test result at screening and no other evidence of active TB may be rescreened once and enrolled according to the following requirements:

- after receiving at least 4 weeks of appropriate ongoing prophylactic therapy for latent TB as per local standard of care

- no evidence of treatment hepatotoxicity (ALT and AST levels must remain  $\leq 2X$  ULN) upon retesting of serum ALT and AST levels before randomization

Such subjects must continue and complete appropriate latent TB therapy during the course of the study to remain eligible and must continue to meet all other inclusion and exclusion criteria for participation.

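### The hepatic monitoring trigger in Protocol 9.4.5 omits AST, so five 8.1.1 criteria can be met without it firing, and no SAP table joins aminotransferase and bilirubin rises

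*Protocol*

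**What the plan says.** **Trigger.** Protocol 9.4.5 asks the investigator to start monitoring, and to consult the sponsor's clinical research physician about follow-up tests, when a subject has "elevated ALT $\geq 3X$ ULN, ALP $\geq 3X$ ULN, or elevated TBL $\geq 2X$ ULN, clinical and laboratory monitoring should be initiated". AST appears in that section only for hepatitis B core antibody positive subjects: "any enrolled subject who is HBcAb+ and who experiences an elevated ALT or AST level" above 3X ULN must have HBV DNA testing.

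**Stopping criteria.** Protocol 8.1.1 lists conditions under which stopping drug is to be considered after consultation with the medical monitor. They include:

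- a single high value, with either enzyme more than eight times ULN
- a sustained rise, worded as "alanine aminotransferase or AST >5X ULN for more than 2 weeks"
- a combined finding, in which bilirubin or PT completes the criterion: "alanine aminotransferase or AST >3X ULN and total bilirubin level (TBL) >2X ULN or prothrombin time >1.5X ULN"
- either enzyme above 3X together with listed symptoms or eosinophilia
- a symptomatic ALP rise: "alkaline phosphatase >2.5 ULN with the appearance of fatigue, nausea, vomiting, right quadrant pain or tenderness" (further listed findings are fever, rash and eosinophilia)

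**Other aminotransferase rules.** Inclusion criterion [7] covers both enzymes ("serum creatinine, aminotransferase (ALT), and aspartate aminotransferase (AST) levels"). So does the TB-prophylaxis rule in 9.4.4.1 ("no evidence of treatment hepatotoxicity (ALT and AST levels must remain" at or below 2X ULN).

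**SAP 6.12.4.1.** ALT and AST are each tabulated at 3X, 5X and 10X ULN, and total bilirubin at 2X, each split by its own baseline. Graphical profiles are made for ALT or AST of at least 5X or ALP of at least 2X. The review of how close aminotransferase and bilirubin rises are in time is confined to profiled patients.

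**The concern.** A monitoring rule should fire no later than the rule for considering withdrawal of drug. Here a subject can reach a withdrawal criterion on AST, or on ALP with symptoms, without the monitoring rule ever firing. The general 9.4.5 trigger is the only aminotransferase rule in the two documents that names ALT without AST, which suggests an oversight.

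On the analysis side, aminotransferase above 3X with bilirubin above 2X is a combination that 8.1.1 itself singles out. Separate tables cannot show whether the two rises occurred in the same person.

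At stake are prompt follow-up of an isolated AST rise and a complete hepatic safety read-out.

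**Working it through.** The plan gives no figure of its own here. The check compares the written rules and the visit schedule.

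**1. Trigger against stopping criteria** (multiples of ULN). The trigger is ALT ≥3 or ALP ≥3 or TBL ≥2. Take ALT <3, ALP <3 and TBL <2, so that it is silent. Splitting the bilirubin and PT alternatives gives eight criteria in 8.1.1. 'Symptoms' stands for the 8.1.1 list, including eosinophilia.

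| 8.1.1 criterion | Can be met while the trigger is silent? |
|---|---|
| ALT or AST >8 | Yes, through AST |
| ALT or AST >5 for more than 2 weeks | Yes, through AST |
| ALT or AST >3 with TBL >2 | No, TBL ≥2 fires |
| ALT or AST >3 with PT >1.5 | Yes, through AST |
| ALT or AST >3 with symptoms | Yes, through AST |
| ALP >3 | No, ALP ≥3 fires |
| ALP >2.5 with TBL >2 | No, TBL ≥2 fires |
| ALP >2.5 with symptoms | Yes, for ALP >2.5 to <3 |

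Five of eight can be met. Enumerating a grid of ALT, AST, ALP, TBL, PT, symptoms and persistence on both sides of each cut-off gives the same five and no others.

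**2. Which of the five need a further test.** AST >8, AST >3 with symptoms and ALP >2.5 with symptoms can be recognised from the chemistry or blood-count result and the clinical picture, and 8.1.1 then calls for the medical monitor. AST >5 for more than 2 weeks needs a repeat draw. AST >3 with PT >1.5 needs a PT, which is absent from the routine list in Appendix 2 and appears only in Appendix 4. The Schedule of Activities leaves unscheduled chemistry to the investigator's discretion.

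**3. Scheduled chemistry** (Protocol Section 2).

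- Post-baseline draws to Week 104: Weeks 2, 4, 8, 12, 16 (5); every 4 weeks from 20 to 52 (9); 64, 80, 96, 104 (4). Total 18 draws, 17 gaps.
- Gaps: one of 2 weeks, twelve of 4 weeks, then 12, 16, 16 and 8 weeks. Check: 2 + 48 + 52 = 102 = 104 − 2.
- The four long gaps total 12 + 16 + 16 + 8 = 52 weeks; 52/102 = 51%.

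So an AST above 5X first seen at Week 52, 64, 80 or 96 has no scheduled repeat for 8 to 16 weeks, against a criterion of more than 2 weeks.

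**4. SAP profile rule.** A profile needs ALT or AST ≥5, or ALP ≥2. For ALT or AST of 3 to <5 with TBL ≥2, the first condition fails, so the result depends on ALP alone: a profile if ALP ≥2, none if ALP <2. In the second case no table fills the gap, because ALT, AST and TBL are never cross-classified.

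**5. Does the fix close the gaps?** ALT or AST ≥3 covers the four AST criteria, and ALP >2.5 with symptoms covers the fifth. Adding ALT or AST ≥3 with TBL ≥2 to the profile rule covers step 4.

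**The case against.** **The best case for leaving the text alone.** Section 8.1.1 already requires consultation once a criterion is met. Protocol 9.2 requires investigators to document review of every laboratory safety report and to follow medically important events until they resolve, stabilise or are explained. Appendix 4 applies to any treatment-emergent hepatic abnormality, so an isolated AST rise is within its wording, and its tests may be required in consultation with the sponsor's physician. When 9.4.5 does fire, it sets no repeat interval and mandates no PT. Adverse events are reviewed at every visit, so the symptom criteria do not wait for chemistry.

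All of that stands, and it limits the gap. It does not supply what the trigger adds: a directed start to monitoring and an early consultation for an isolated AST rise, before persistence or PT is known.

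**Stronger readings the documents do not support.**

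- A reader might infer that subjects meeting the five criteria go unmanaged, or that 8.1.1 mandates stopping. It calls for consultation and for stopping to be considered.
- A reader might extend the schedule count to Week 120, giving (52 + 16)/(102 + 16) = 68/118 = 58%. No dosing visit is scheduled in this study after Week 104, so a rule about stopping drug has nothing left to act on.
- A reader might infer that every aminotransferase of 3X to 5X with raised bilirubin escapes profiling. Those with ALP of at least 2X are profiled, and all with TBL of at least 2X trigger 9.4.5 monitoring.
- A reader might infer that such liver cases vanish from the report. Profiles span all phases, hepatic-disorder query tables are planned, and adverse events and high/low laboratory results are reported beyond Induction.

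**Conclusion.** The inconsistency is real and minor: a cheap improvement. With ALT <3X, ALP <3X and TBL <2X, five of the eight 8.1.1 criteria can be met without the 9.4.5 trigger firing. The practical gap is mainly AST >5X sustained and AST >3X with prolonged PT, where long intervals between scheduled draws cover 52 of the 102 weeks from Week 2 to Week 104. In the SAP the gap is ALT or AST of 3X to <5X with TBL ≥2X and ALP <2X.

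This rests on reading the PT limb of 8.1.1 as joined to ALT or AST >3X, and on scheduled draws only. The documents give no basis for estimating how many subjects would be affected. No efficacy result or error rate changes.

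**What to change.** - **Protocol 9.4.5:** replace the ALT ≥3X limb with ALT or AST ≥3X, and add ALP >2.5X with symptoms, using the 8.1.1 list.
- **SAP 6.12.4.1:** add one table of subjects with ALT or AST ≥3X together with TBL ≥2X, and prepare profiles for subjects meeting that combination.

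The cost is one changed protocol sentence that uses the existing Appendix 4 panel, plus one table and a few profiles from data already collected. The downside is a few extra work-ups for AST rises of muscle origin; creatine kinase, already in the Appendix 2 chemistry panel, helps to sort these. The change prompts monitoring and consultation but does not itself fix a repeat interval or require a PT; those stay with the investigator and the sponsor's physician.

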## 9.5. Pharmacokinetics

At the visits and times specified in the Schedule of Activities (Section 2), venous blood samples will be collected to determine the serum concentrations of LY3074828.

A maximum of 3 samples may be collected at additional time points during the study if warranted and agreed upon between both the investigator and sponsor. Instructions for the collection and handling of blood samples will be provided by the sponsor. The actual date and time (24-hour clock time) of each sampling will be recorded.

Drug concentration information that may unblind the study will not be reported to investigative sites or blinded personnel.

Bioanalytical samples collected to measure investigational product concentration will be retained for a maximum of 1 year following last patient visit for the study.

## 9.6. Pharmacodynamics

Not applicable.

## 9.7. Pharmacogenomics

### 9.7.1. Whole Blood Sample for Pharmacogenetic Research

A whole blood sample will be collected for pharmacogenetic analysis as specified in the Schedule of Activities (Section 2) where local regulations allow.

Samples will not be used to conduct unspecified disease or population genetic research either now or in the future. Samples will be used to investigate variable response to LY3074828 and to investigate genetic variants thought to play a role in psoriasis. Assessment of variable response may include evaluation of AEs or differences in efficacy.

All samples will be coded with the subject number. These samples and any data generated can be linked back to the subject only by the investigator site personnel.

Samples will be retained for a maximum of 15 years after the last subject visit for the study, or for a shorter period if local regulations and/or ERBs/investigational review boards (IRBs) impose shorter time limits, at a facility selected by Lilly or its designee. This retention period enables use of new technologies, response to regulatory questions, and investigation of variable response that may not be observed until later in the development of LY3074828 or after LY3074828 becomes commercially available.

Molecular technologies are expected to improve during the 15-year storage period and therefore cannot be specifically named. However, existing approaches include whole genome or exome sequencing, genome wide association studies, and candidate gene studies. Regardless of technology utilized genotyping data generated will be used only for the specific research scope described in this section.

## 9.8. Biomarkers

Biomarker research is performed to address questions of relevance to drug disposition, target engagement, pharmacodynamics (PD), mechanism of action, variability of subject response (including safety), and clinical outcome. Sample collection is incorporated into clinical studies to enable examination of these questions through measurement of biomolecules including DNA, ribonucleic acid (RNA), proteins, lipids, and other cellular elements.

CCI [REDACTED] will be collected at the times specified in the Schedule of Activities (Section 2) where local regulations allow.

Samples will be used for research on the drug target, disease process, variable response to LY3074828, pathways associated with psoriasis, mechanism of action of LY3074828, and/or research method or in validating diagnostic tools or assay(s) related to psoriasis.

All samples will be coded with the subject number. These samples and any data generated can be linked back to the subject only by the investigator site personnel.

Samples will be retained for a maximum 15 years after the last subject visit for the study, or for a shorter period if local regulations and ERBs impose shorter time limits, at a facility selected by Lilly or its designee. This retention period enables use of new technologies, response to regulatory questions, and investigation of variable response that may not be observed until later in the development of LY3074828 or after LY3074828 becomes commercially available.

Skin biopsies from lesional skin at baseline will be required of all subjects according to the Schedule of Activities (Section 2). A local anesthetic will be applied, and 4-mm punch skin biopsies will be obtained from where a psoriatic lesion was in existence at baseline according to the Schedule of Activities. Detailed instructions for handling the biopsies at the study site will be provided by the sponsor. Skin biopsies will be used to understand the mechanism of action of the test drug. Exploratory analysis of biomarker data that comes from testing of the biopsies may be analyzed in relation to the clinical outcome, with a view to possible identification of baseline markers that predict response and to investigate the observed long lasting response to treatment.

### 9.8.1. Samples for Immunogenicity Research

Blood samples for immunogenicity testing will be collected to determine antibody production against the investigational product as specified in the Schedule of Activities (Section 2). Immunogenicity will be assessed by a validated assay designed to detect ADAs in the presence of the investigational product (drug-tolerant ADA assay). Antibodies may be further characterized and/or evaluated for their ability to neutralize the activity of the investigational product (neutralizing ADA assay).

Samples will be retained for a maximum of 15 years after the last subject visit for the study, or for a shorter period if regulations and ERBs impose shorter time limits, at a facility selected by

Lilly or its designee. The duration allows the sponsor to respond to future regulatory requests related to the investigational product.

### **9.9. Health Economics**

Health economics and medical resource utilization parameters will not be evaluated in this study.

## 10. Statistical Considerations

### 10.1. Sample Size Determination

Approximately 200 subjects will be randomized at a 1:1:1:1 ratio in the blinded induction dosing period to LY3074828 30 mg, 100 mg, 300 mg, and placebo (50 subjects per dosing regimen, respectively). Randomization will be stratified by prior exposure to biologic therapy for psoriasis (yes/no).

CCI

### 10.2. Populations for Analyses

For purposes of analysis, the following populations are defined:

Population	Description
Intent-to-treat (ITT)	All randomized subjects, even if the subject does not take the assigned treatment, does not receive the correct treatment, or otherwise does not follow the protocol. Subjects will be analyzed according to the treatment to which they were assigned. Unless otherwise noted, efficacy and health outcomes analyses for the induction period will be conducted on this population.
Safety	All randomized subjects who received at least 1 dose of study treatment. Subjects will be analyzed according to the treatment to which they were assigned. Safety analyses for the induction period will be conducted on this population.
Maintenance period	All ITT subjects who received at least 1 dose of study treatment and have entered the maintenance period at Week 16 (Visit 7). Efficacy, health outcomes, and safety analyses for the maintenance period will be conducted on this population.
Follow-up	All ITT subjects who received at least 1 dose of study treatment and have entered the post-treatment follow-up period. Subjects will be analyzed according to the last treatment they received before entering the post-treatment follow-up period. Efficacy, health outcomes, and safety analyses for the post-treatment follow-up period will be conducted on this population.

Abbreviation: ITT = intent-to-treat.

Additional analysis populations will be described in the statistical analysis plan (SAP) as deemed appropriate.

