### Objective(s)/Endpoints:

Objectives	Endpoints

Primary
 
To test the hypothesis that treatment with LY3074828 is superior to placebo in inducing PASI 90 response at Week 16 in subjects with moderate-to-severe plaque psoriasis
	
The proportion of subjects achieving PASI 90 at Week 16 (NRI)

Secondary
 
 
To evaluate the safety and tolerability of treatment with LY3074828
 
To evaluate the efficacy of treatment with LY3074828 compared to placebo in inducing PASI 100 and PASI 75 at Week 16
 
To evaluate the efficacy of treatment with LY3074828 compared to placebo in inducing sPGA 0 (clear) and sPGA 0/1 at Week 16
 
To evaluate the effect of LY3074828 on patient reported outcome measures: PSS, PatGA, DLQI, and SF-36 at Week 16
 
To characterize the long-term efficacy of LY3074828 on the PASI 100, PASI 90, and PASI 75 responses at Week 52, 104, and 120
 
To characterize the long-term efficacy of LY3074828 on patient reported outcome measures PSS, PatGA, DLQI, and SF-36 at Weeks 52, 104, and 120
 
To characterize the PK of LY3074828
 
	
 
Adverse event and discontinuation rates
 
The proportion of subjects achieving PASI 100 and PASI 75 at Week 16 (NRI)
 
The proportion of subjects achieving sPGA 0 and sPGA 0/1 at Week 16 (NRI)
 
The mean change from baseline for PSS, PatGA, DLQI, and SF-36 at Week 16
 
The proportion of subjects achieving PASI 100, PASI 90, and PASI 75 at Weeks 52, 104, and 120
 
The mean change from baseline for PSS, PatGA, DLQI, and SF-36 at Weeks 52, 104, and 120
 
Clearance and volume of distribution
 

Abbreviations: DLQI = Dermatology Life Quality Index; NRI = nonresponder imputation; PASI = Psoriasis Area and Severity Index; PASI 75 = 75% improvement in PASI from baseline; PASI 90 = 90% improvement in PASI from baseline; PASI 100 = 100% improvement in PASI from baseline; PatGA = Patient Global Assessment; PK = pharmacokinetics; PSS = Psoriasis Symptom Scale; SF-36 = Short-Form Health Survey; sPGA = static Physician's Global Assessment.

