### 7.8.2. Special Treatment Considerations

Subjects in the maintenance PRN dosing arm may receive blinded rescue treatment with 300 mg Q8W. Rescue treatment may occur if not regaining a PASI  $\geq 90$  after 3 consecutive doses of retreatment or if a subject is below a PASI 50 following 1 retreatment dose. A subject starting rescue treatment will remain on that regimen through the end of the study regardless of any subsequent changes in PASI score.

All biological agents carry the risk of an injection site and/or hypersensitivity general reaction. Therefore all subjects should be closely monitored for signs or symptoms that could result from such reactions. Sites should have appropriately trained medical staff and appropriate medical equipment available when subjects are receiving study drug. If a subject experiences an acute hypersensitivity reaction after an injection of study drug, he or she should receive appropriate supportive care.

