### 10.3.3.2. Secondary Analyses

Treatment comparisons between each LY3074828 dose regimen (30 mg, 100 mg, 300 mg) and placebo at Week 16 in the proportion of subjects achieving PASI 100, PASI 75, sPGA 0 (clear), and sPGA 0/1 will be analyzed using logistic regression with NRI as described in Section 10.3.1.1. The proportion and 95% confidence interval of subjects achieving PASI 100, PASI 90, and PASI 75 at Weeks 52, 104, and 120 will be summarized by treatment.

Treatment comparisons between each LY3074828 dose regimen (30 mg, 100 mg, 300 mg) and placebo in the change from baseline to Week 16 in health outcome measures DLQI, SF-36, CCI will be analyzed using the MMRM model as described in Section 10.3.1.1. The change from baseline and 95% confidence interval for health outcome measures DLQI, SF-36, and PatGA at Weeks 52, 104, and 120 will be summarized by treatment.

The Week 120 (Visit 804) data will be summarized by including only subjects who both enter and complete the post-treatment follow-up period of Study AMAF.

CCI

C  
C  
I

[Redacted text block containing multiple lines of blacked-out content]

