6.1.1. Subject Populations for Analyses

For purposes of analysis, populations for analyses are described in [Table 6.1](#).

Table 6.1. Subject Populations for Analyses

Population	Description
Intent-to-treat (ITT) (Induction Period Efficacy)	All randomized subjects, even if the subject does not take the assigned treatment, does not receive the correct treatment, or otherwise does not follow the protocol: 
 Unless otherwise noted, efficacy and health outcomes analyses for the Induction Period will be conducted on this population. Subjects will be analyzed according to the treatment to which they were assigned.
Induction Period Safety	All randomized subjects who received at least 1 dose of study treatment: 
 Unless otherwise noted, safety analyses for the Induction Period will be conducted on this population. Subjects will be analyzed according to the treatment to which they were assigned.
Maintenance Period Efficacy	All randomized subjects who have entered the Maintenance Period (see definition of entering Maintenance Period in Section 6.1.2.1): 
 Unless otherwise noted, efficacy, and health outcomes for the Maintenance Period will be conducted on this population. Subjects will be analyzed according to the treatment to which they were assigned in Maintenance Period.

Population	Description
Maintenance Period Safety	
All randomized subjects received at least 1 dose of study treatment who have entered the Maintenance Period (see definition of entering Maintenance Period in Section 6.1.2.1):
 
 • Unless otherwise noted, safety analyses for the Maintenance Period will be conducted on this population. • Subjects will be analyzed according to the treatment to which they were assigned in Maintenance Period, with all LY3074828 300 mg Q8W arms combined, that is, there will be 4 treatment groups in the Maintenance Period: 
 ○ LY 300 mg PRN ○ LY 100 mg PRN ○ LY 30 mg PRN ○ LY 300 mg Q8W (including subjects from 4 Induction Period treatment groups)

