6.3. Handling of Dropouts or Missing Data

6.3.1. Non-Responder Imputation (NRI)

Analysis of categorical efficacy and health outcome variables will be assessed using a NRI method. Subjects will be considered a non-responder for the NRI analysis if they do not meet the clinical response criteria or have missing clinical response data at the analysis time point. Randomized subjects without at least 1 postbaseline observation will also be defined as non-responders for the NRI analysis.

Due to the design, PRN subjects who got rescued will get a different treatment (300 mg LY SC Q8W), therefore the subsequent visits following the first dose of rescue treatment will be defined as non-responders in the analysis for the Maintenance Period.

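### Rescued PRN subjects count as failures in their PRN arm at Weeks 52 and 104 but leave that arm at Week 120, so the PRN response series mixes off-drug change with removal of selected failures

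*Protocol*

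**What the plan says.** The endpoint is a single series. The Protocol Synopsis lists "The proportion of subjects achieving PASI 100, PASI 90, and PASI 75 at Weeks 52, 104, and 120", and Protocol 10.3.3.2 reports the proportions "achieving PASI 100, PASI 90, and PASI 75 at Weeks 52, 104, and 120 will be summarized by treatment".

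**Weeks 52 and 104.** SAP Table 6.1 (section 6.1.1) sets the Maintenance efficacy grouping: "Subjects will be analyzed according to the treatment to which they were assigned in Maintenance Period". SAP 6.3.1 adds that, for rescued PRN subjects, "the subsequent visits following the first dose of rescue treatment will be defined as non-responders in the analysis for the Maintenance Period".

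**Rescue.** Protocol 7.8.2: "Subjects in the maintenance PRN dosing arm may receive blinded rescue treatment with 300 mg Q8W", and "A subject starting rescue treatment will remain on that regimen through the end of the study". Eligibility is failure to get back to PASI 90 after three retreatment doses in a row, or a response under PASI 50 after one.

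**Week 120.** The Follow-up row of Protocol 10.2 covers efficacy as well as safety and states: "Subjects will be analyzed according to the last treatment they received before entering the post-treatment follow-up period". Protocol 10.3.3.2 restricts the Week 120 data by "including only subjects who both enter and complete the post-treatment follow-up period". Under Protocol 5.1 and 7.8.3, subjects who finish Week 104 may go to a separate extension study instead of follow-up.

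**What the SAP adds on follow-up.** SAP 6.1.2.1 defines follow-up membership by having had Visit 29. Table 6.1 has no follow-up row, Table 6.3 has no Week 120 time point, and no rule carries rescue status into follow-up.

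**The concern.** The same subject can be a failure in a PRN arm at Week 104 and absent from that arm at Week 120, within one endpoint. The subjects who leave are not a random subset: rescue is open only to those who did poorly on PRN retreatment. Taking them out raises the Week 120 PRN rate relative to Week 104, and raises it most in the arm with the most rescue.

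Protocol 5.1 says follow-up is there to assess safety and efficacy, and SAP 5.2 says PRN results will support the Phase 3 maintenance dosing strategy. A reader will naturally compare Week 104 with Week 120 in each PRN arm. A flat line could mean that response persists without further dosing, or that losses were offset by failures leaving the denominator. The planned summary does not let the reader separate the two.

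**Working it through.** The documents give no figure for this point: no rescue rate, no extension roll-over rate and no projected Week 120 rate. The shares below are therefore assumptions. The only stated figure used is the 60% Week 16 PASI 90 rate in SAP 5.2. With 50 per arm it gives 50 x 0.60 = 30 PRN entrants, used only as a convenient arm size. (The over-99% power stated there reproduces, at above 99.99% by exact calculation, but has no bearing here.)

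**Can rescue come early enough to matter?** Yes. PRN dosing can start at Week 20. At 8-week spacing, one retreatment dose leads to about Week 28 and three doses (Weeks 20, 28, 36) to about Week 44, both before Week 52.

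**Notation, for one PRN arm.**
- m: PRN-assigned subjects who enter and complete follow-up
- k: the number of these who were rescued, so r = k/m
- R: non-rescued PASI 90 responders at Week 104
- L: the share of R that loses response by Week 120 (no new responders assumed)

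**Formulas.**
- Week 104, assigned arm, rescued = non-responder: R/m
- Week 120, last treatment received: R(1-L)/(m-k)
- Week 120, assigned arm, rescued = non-responder: R(1-L)/m
- Ratio of the two Week 120 rates: m/(m-k) = 1/(1-r)
- Apparent change from Week 104 is zero when (1-L)/(m-k) = 1/m, that is, when L = r

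**Worked case.** Let m = 30, k = 6, R = 20, with all 30 completing follow-up.
- Week 104: 20/30 = 66.7%.
- Four of the 20 responders lose response. By last treatment, Week 120 = 16/24 = 66.7%, an apparent change of zero. On the kept denominator it is 16/30 = 53.3%, a fall of 13.3 points.
- Nobody loses response. By last treatment, Week 120 = 20/24 = 83.3%, an apparent rise of 16.7 points.

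**Range.** m = 30, about 80% of non-rescued subjects responding at Week 104, rounded to whole subjects:

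| Rescued k (r) | Factor 1/(1-r) | R | Week 104, R/30 | Week 120 by last treatment, no loss | Loss L that shows as no change | Fall on kept denominator at that L |
|---|---|---|---|---|---|---|
| 3 (10%) | 1.11 | 22 | 73.3% | 22/27 = 81.5% | 10% | 7.3 points |
| 6 (20%) | 1.25 | 19 | 63.3% | 19/24 = 79.2% | 20% | 12.7 points |
| 9 (30%) | 1.43 | 17 | 56.7% | 17/21 = 81.0% | 30% | 17.0 points |

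**The second selection.** Return to the worked case, but let all 6 rescued subjects enter the extension study. The 24 completers contain no rescued subject, so r = 0 and both groupings give 16/24 = 66.7% at Week 120. Yet the Maintenance table still shows 20/30 = 66.7% at Week 104. On the same 24 subjects, Week 104 is 20/24 = 83.3%, so the fall is 16.7 points. Changing the grouping alone would not reveal it; both weeks must be shown on the same subjects.

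**The case against.** Grouping by last treatment is a prespecified and reasonable choice for an off-drug period, because persistence of response depends on the regimen last received. Scoring a subject who is clear at Week 120 after a long spell on 300 mg Q8W as a failure of 30 mg PRN answers a different question, namely success of the PRN strategy. This stands: the last-treatment table should not be called wrong or dropped.

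Week 120 is also openly a selected set. The completers-only rule and the extension study change the denominator whatever the grouping, in an unknown direction. This stands too, and it is why same-subject reporting is part of the fix.

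No Week 104 to 120 contrast is planned, the summaries are descriptive, SAP 6.1 requires group sizes to be shown, and rescued subjects have their own Rescue Period summaries. An attentive reader would see the denominator shrink, so concealment would be too strong a word. Group sizes alone would not, however, let that reader reconstruct the rate with rescued subjects kept in.

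A reader might infer two stronger things that the documents do not support. One is that rescued subjects necessarily join, and so alter, the 300 mg Q8W group at Week 120. Protocol 10.2 names no follow-up groups, and SAP Tables 5.1 and 6.1 treat rescue as its own regimen and population, so a separate rescue group is equally possible. The other is that the PRN rate will show a spurious rise of a definite size, for example 7, 14 or 21 points for 10%, 20% or 30% rescued with 70% of the rest responding. That needs every PRN subject to enter and complete follow-up, and it needs a rescue share that neither document gives. Rescue is also optional.

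**Conclusion.** The inconsistency is real and neither document reconciles it. Within one secondary endpoint, rescued PRN subjects are failures in their assigned arm at Weeks 52 and 104 and leave that arm at Week 120; where they go is not stated. Among follow-up completers the Week 120 PRN rate is multiplied by 1/(1-r): 1.11, 1.25 or 1.43 at an assumed 10%, 20% or 30% rescued. A loss of response in up to a share r of responders then shows as no change or as a rise, when the same subjects are compared with rescue scored as failure at Week 104. The effect is nil if no completer was rescued, either because rescue was not used or because all rescued subjects entered the extension study.

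Two limits apply. In the 300 mg PRN arm rescue changes the regimen and not the dose, so subjects leave that group only if groups are defined by regimen, as Table 6.1 does for Maintenance safety. And the net bias of the published series is unknown, because roll-over and completion also act on it.

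The primary endpoint and all comparisons with placebo are untouched. This is a cheap improvement of low to moderate priority.

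**What to change.** In the SAP:
1. Add a Week 120 PASI 75/90/100 summary by Maintenance-assigned arm, with rescued PRN subjects kept as non-responders.
2. Show Week 104 beside it on the same follow-up completers, with the same grouping and rescue rule, and name this pair as the basis for any Week 104 to Week 120 reading.
3. Keep the last-treatment grouping for follow-up safety and as a labelled efficacy table, and state whether rescued subjects appear under 300 mg Q8W or as a separate rescue group.
4. For the patient-reported outcomes, which at Week 120 are mean changes, use the same grouping and the same subjects at Weeks 104 and 120, with post-rescue values handled as in the Maintenance analysis. SAP 6.3.2 states that handling (visits before rescue only) for the MMRM, while Table 6.3 lists ANCOVA for these outcomes, so the sentence should cover both.

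The cost is a few lines of SAP text and one more table for PASI, with its counterpart for the patient-reported outcomes. No new data are needed and conduct does not change. The PRN rates at Week 120 will look less favourable where rescued subjects complete follow-up.
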